The long-term goal of the ENLACE is to reduce obesity and obesity-related morbidity and mortality by increasing the number of Latinas who meet national PA guidelines for adults9. We hypothesize that Latinas at the PA intervention sites will significantly increase their MVPA levels as a result of addressing their specific individual and environmental barriers and enhancing their social support and collective efficacy, compared to Latinas at the attention-control sites.

Primary aim: Test the effect of a 16-week, promotora-led PA intervention on minutes per week of MVPA (primary outcome) among Latinas in South Texas, compared to an attention-control group.

Secondary aims: a) Test the effect of the 16-week promotora-led PA intervention on physical fitness and weight maintenance (secondary outcomes); b) assess the maintenance of primary and secondary outcomes 6 months after the end of the intervention; c) examine the role of self-efficacy for PA, social support, decisional balance, and collective efficacy as mediators of changes in MVPA; and d) evaluate the impact of Latinas' social and community environment context on their success (or failure) in increasing MVPA and maintaining the behavior change.

Eight community resource centers (CRCs) in four Lower Rio Grande Valley (LRGV) counties—Starr, Hidalgo, Willacy and Cameron—will be randomly assigned to either the ENLACE PA Intervention (4 CRCs) or the attention-control condition (4 CRCs). We will recruit 864 Latinas ages 18 - 64 who do not meet national PA guidelines from colonias (unincorporated settlements where many people live in impoverished conditions and lack basic services) in the service area of the eight CRCs. Participants from CRCs randomized to the ENLACE PA Intervention (N = 432; 108 women per CRC) will receive the 16-weekly promotora-led group sessions, followed by 24 weeks of a maintenance intervention (monthly promotora-delivered newsletter and bi-monthly telephone counseling). The goal for the 16 weeks will be for women to engage in 30 minutes per day of MVPA on 5 or more days per week. The attention-control group (N = 432; 108 women per CRC) will receive 8 promotora-led group sessions twice a month on home safety/first aid and monthly generic health education materials during the maintenance intervention period. Standardized measurement of primary and secondary outcomes will occur at baseline, immediate (16 weeks) and delayed (40 weeks) post-intervention.

2. Background.

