D.2.4.2. ENLACE PA Intervention Activities. Consistent with national PA guidelines, participants randomized to the *ENLACE* PA intervention will be encouraged to engage in moderate to vigorous intensity PA for 30 minutes on 5 or more days per week. The *promotora*-led intervention will consist of 16 weekly sessions that include 30 minutes of group health education plus 30-45 minutes of group exercise. The sessions address the determinants of knowledge, perceived barriers and benefits, behavioral skills, self-efficacy, reinforcement and social support for the behavioral outcome of increasing MVPA. Didactic approaches include information provision, discussion, active learning, guided practice, self-reevaluation, and modeling. Participants will receive a pedometer and a set of resistance bands (3 resistance levels). *Promotoras* will demonstrate the use of pedometers, walking techniques, strength exercises with resistance bands, and self-assessment of exercise exertion level. Participants will start their PA program slowly, gradually increasing both frequency and intensity over the 16 weeks in order to meet the study goal. Pedometers will be used as a PA self-monitoring and motivational enhancement tool. The *promotora* will advocate using steps per day as part of goal setting activities (e.g., focusing on increasing steps per day through bouts of walking). Women in the *ENLACE* pilot preferred (1) incorporating group exercise as a part of the health education sessions and (2) brisk walking and Zumba[®]. *Promotoras* will be trained to lead group exercise activities and will have access to an exercise DVD library, resistance bands, and yoga mats. These PA options and resources will also be available at the CRCs for participants’ use outside the scheduled intervention sessions. In addition, *promotoras* will use the Volunteer Walk Leader Manual to recruit and train a cadre of volunteers to lead walking groups at the CRC. This manual, developed at the University of South Carolina, was translated into Spanish for use in the pilot study. (A copy of the manual is in Appendix C.)

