Primary Outcomes (Aim 1 & Aim 2b). MVPA outcomes will be self-reported behavior of a typical week measured with the CHAMPS instrument (minutes/week MVPA) and objective measurement from the accelerometer (minutes/day MVPA). Averages for each MVPA outcome at each time-point will be calculated and compared for the intervention versus the attention-control group and ANOVA tests will be performed to evaluate for significant differences between groups. Assessment will be made to determine direction- e.g. increases or decreases- of change between baseline and post-intervention, and baseline and 6-month follow-up. Using STATA 11 to conduct our modeling we will use a regression that is both multilevel and temporal in nature. Mixed-effects regression can be conducted using the `xreg`, `xtgee` and `xtlogit` command in STATA 11 SE¹⁰², depending on the structure of the outcome variable. In this case, time-points of measurement are nested within subjects in a random intercept model. Random coefficient modeling will be conducted using random effects variables at level 2 (subject level) that will be both fixed (nativity, occupation, education, baseline age, etc.) and time varying (perceptions over time, behavior over time, income). Below we represent the equation for a binomial outcome model

$$\log(\mu_{ij}) = x'_{ij} \beta_1 + x'_{ij} \beta_2 \quad (i = \text{level 1-repeated MVPA measures over time}, j = \text{level 2- Individual level covariates})$$

Whereas β_{ij} represents the expected change in the log of the mean unit change of x_{ij} A one unit change in x_{ij} corresponds to an increase β_{ij} in the log of the average.

Secondary Outcomes (Aim 2a). Similar methodology will be implemented in this analysis as in AIM 1. Our outcome variables

FORM C

IRB #	HSC20110460H
-------	--------------

for aspect of the study will be physical fitness, BMI and anthropometric measures of body fat. Averages for physical fitness, BMI and body fat will be calculated for intervention versus the attention-control group and ANOVA tests will be conducted to evaluate significant cross-sectional differences between the intervention and attention-control groups. Evaluation of temporal changes between each time-point will be made. Mixed effect regression models will be conducted as described in Aim 1.

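### The Aim 1/2b regression, reused for Aim 2a, adjusts for perceptions and behaviour measured after randomisation, so its arm effect is not the total effect that Aim 1 asks for

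*Protocol*

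**What the plan says.** Aim 1 (Protocol, section 1) is stated as: "Test the effect of a 16-week, promotora-led PA intervention on minutes per week of MVPA (primary outcome"), compared with attention control. That is a total effect.

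The analysis is in section 6.a, Primary Outcomes (Aim 1 & Aim 2b). It first plans ANOVA comparisons of the arms at each time point, with no covariates mentioned. It then plans a multilevel regression: "Random coefficient modeling will be conducted using random effects variables at level 2 (subject level"). These variables are said to be both fixed (nativity, occupation, education, baseline age and so on) "and time varying (perceptions over time, behavior over time, income"). The key under the displayed equation calls them "level 2- Individual level covariates". For fitness, BMI and body fat (Aim 2a) the protocol adds: "Mixed effect regression models will be conducted as described in Aim 1".

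Three other places bear on what those time-varying terms are:

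- The hypothesis in section 1 expects MVPA to rise "as a result of addressing their specific individual and environmental barriers and enhancing their social support and collective efficacy".
- Secondary aim (c) is to "examine the role of self-efficacy for PA, social support, decisional balance, and collective efficacy as mediators of changes in MVPA".
- Section D.2.4.2 describes the programme content: "The sessions address the determinants of knowledge, perceived barriers and benefits, behavioral skills, self-efficacy, reinforcement and social support".

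The Mediator Variables list and table 6.d place self-efficacy, social support, benefits and barriers, collective efficacy and perceptions of environmental supports among the mediator variables. Table 6.d has them measured three times.

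**The concern.** A covariate followed over baseline, 16 and 40 weeks takes two of its three values after randomisation. If the intervention moves that covariate and the covariate moves MVPA, holding it constant removes that route from the arm coefficient. What remains answers a different question from Aim 1: how much the programme changes MVPA apart from its effect on the adjusted variables.

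There is a second difficulty. Post-randomisation perceptions and MVPA can share causes that randomisation does not balance once one conditions on the perceptions. The adjusted coefficient therefore need not even be a clean direct effect.

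For Aim 2a the same models would adjust fitness, BMI and body fat for behaviour over time. If that term covers activity or diet, it is an obvious route to those outcomes. If it covers physical activity in the MVPA model, the outcome is partly adjusted for itself.

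At stake is whether the planned regression can deliver the trial's main answer.

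**Working it through.** **1. Is the adjustment stated, or inferred from silence?** It is stated. The same sentence specifies age at baseline but perceptions and behaviour over time, so the text itself separates baseline from follow-up values. Nothing in the protocol restricts the regression to baseline covariates or names a model without the time-varying terms.

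**2. Are the covariates on the causal path?** The perception scales appear under Mediator Variables, the sessions target several of them, and the hypothesis attributes the MVPA gain to changes of this kind. Section 6.a, Mediation Analyses (Aim 2c), has a second model that regresses change in MVPA on group plus change in the mediator. The group coefficient there is a direct effect. The Aim 1 regression conditions in the same way.

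**3. The plan's own figure.** Inputs from Power and Sample Size are effect 0.50 SD, ICC .01, power 0.80 and 83 per site; from section 1, 4 v 4 centres. No alpha is given.

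SE = sqrt(2 × (0.01 + 0.99/83) / 4) = 0.1047 SD. Noncentrality = 0.50 / 0.1047 = 4.775, with 8 − 2 = 6 df.

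- Two-sided 0.01: power is 0.801 at 83 per site and 0.7985 at 82, so 83 is reproduced.
- Two-sided 0.05: power at 83 is 0.976, and 30 per site would already reach 0.80.

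The 0.01 level is therefore inferred, not documented. Both levels are carried forward.

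**4. Illustration of the loss.** Adjusted effect = 0.50 × (1 − mediated share), with the SE held at 0.1047. The mediated share is an assumption; the protocol gives none.

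| Mediated share | Adjusted effect (SD) | Power, two-sided 0.05 | Power, two-sided 0.01 |
|---|---|---|---|
| 0% | 0.500 | 0.976 | 0.801 |
| 25% | 0.375 | 0.845 | 0.515 |
| 50% | 0.250 | 0.517 | 0.212 |
| 75% | 0.125 | 0.173 | 0.048 |

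**5. Simulation check.** Trials with three visits, 8 centres of 83 women and 300 replicates per setting were analysed by within-subject regression with visit terms. Without the mediator the arm effect came back as 0.50 SD. With the time-varying mediator in the model it was 0.37, 0.25 and 0.13 SD for shares of 25%, 50% and 75%. The simulated mediator and outcome shared no unmeasured cause, so this is the clean direct-effect case. With confounding, the result could lie on either side.

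**The case against.** Several points on the other side stand.

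- **The ANOVA.** The covariate-free ANOVA estimates an unadjusted contrast and does not have this defect. A reader might infer that an effective programme would end up reported as ineffective. That follows only if the regression overrides the ANOVA, and the protocol does not say so. Nor does it say the reverse, and the regression is the only one of the two described as multilevel and temporal.
- **Content of the terms.** Perceptions and behaviour are not itemised. The one instrument with perceptions in its title covers environmental supports. It is listed with the mediator variables but is not among the four mediators named in secondary aim (c). Reading the term as all the perception scales is plausible, not documented. This limits how far the bias can be sized, but it does not make follow-up values suitable covariates.
- **Form of the model.** The displayed equation has no arm or arm-by-time term, and the covariates are introduced as random-effects variables. The wording is loose. If this regression is to test Aim 1, however, it must contain an arm term, and that is the coefficient affected.
- **The power figures.** They use a centre-level SE, whereas the regression described nests visits within women only. With 332 per arm and no centre level, SE = sqrt(2/332) = 0.078 SD, and 50% mediation would leave about 90% power. That SE is too small for a centre-randomised trial, but it shows that the table does not describe the written model exactly. Adjustment would also reduce residual variance, which the table ignores.

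Two stronger readings are tempting. One is that the result would contradict the Aim 2c analysis. It would not: the second Aim 2c model also conditions on the mediator, so a smaller adjusted arm effect agrees with mediation. The other is that the hypothesis implies full mediation and hence an adjusted effect of zero. The hypothesis names mechanisms but gives no proportion.

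**Conclusion.** The point holds for the regression, not for every planned comparison. As written, the Aim 1/2b regression and its Aim 2a counterpart condition on follow-up values of variables that the programme is meant to change. Their arm effect is therefore not the total effect required.

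The expected direction is toward a direct effect. Shrinkage toward zero is not guaranteed, because mediator-outcome confounding can act either way.

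The size cannot be derived from the protocol. The table shows only the order of loss under an assumed mediated share, a fixed centre-level SE and an alpha that the protocol does not state. Because neither the regression nor the ANOVA is named as decisive, the protocol also does not ensure that the unaffected analysis carries the conclusion.

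**What to change.** In section 6.a, Primary Outcomes and Secondary Outcomes:

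- Restrict the main Aim 1, 2a and 2b models to arm, visit, arm-by-visit and variables fixed before the intervention: baseline demographics including income and, if wanted, baseline perceptions.
- Enter the baseline outcome either as a covariate or as one of the repeated outcomes, not both.
- State that this model decides, and give the ANOVA a supporting role.
- Keep post-baseline perceptions and behaviour for Aim 2c, or for a model labelled exploratory.

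This changes a few sentences and needs no new data. The cost is slightly less reduction in residual variance than the time-varying covariates might have given.

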Perceived Stress Scale (PSS-10) examines the degree to which specific situations are deemed as stressful in the past week. The PSS is well validated and has been used in many studies examining the association between stress and health⁹⁵.

Perceptions of Environmental Supports. The 10 items were adapted from the International Physical Activity Prevalence Study (IPS) Self-Administered Environmental Module to assess environmental supports and capture participants' sense of community opportunities for PA.

Food Frequency Questionnaire (FFQ) is approximately a 110 food item questionnaire designed to estimate usual and customary intake of a wide array of nutrients and food groups that is to be conducted by interviewer-administration.

Demographic Variables:

Demographic data (collected at baseline only) will be used to describe the study participants and facilitate statistical analyses where potential confounding by these variables should be controlled. Information will include age, current marital status, educational attainment, acculturation, nativity, current employment status and occupation, household size, family income.

In-Depth Interviews:

Individual in-depth interviews will be conducted with a subset of participants in the PA intervention. The purpose of the interview is to explore participants' personal experiences of behavior change and identified barriers and enablers to success/failure, including intrapersonal, social and environmental influences (Aim 2d). These qualitative data will complement and explicate quantitative findings from the intervention (Aim 2c). All participants in the PA intervention that complete the 16 week immediate post intervention assessment will be in the population to be sampled for the qualitative interviews. After each cohort completes the 16 week assessment, 4 participants per CRC, stratified by success or failure (based on level of improvement in MVPA), will be randomly selected to take part in a two-part series of individual, in-depth interviews (N=64). Participants will be classified as successful if they show a minimum increase of 15 minutes/day MVPA (objectively measured). Each participant selected will be interviewed twice, immediately after the 16 week and 40 week assessments.

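### The regression specified for Aims 1 and 2b, reused for Aim 2a, adjusts for post-randomisation perceptions and behaviour, so an arm effect read from it would not be the total effect that Aim 1 asks for

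*Protocol*

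**What the plan says.** The primary aim (protocol, section 1) is to "Test the effect of a 16-week, promotora-led PA intervention on minutes per week of MVPA (primary outcome"), compared with attention control. The hypothesis in the same section is that MVPA will rise "as a result of addressing their specific individual and environmental barriers and enhancing their social support and collective efficacy". One secondary aim, 2c, is to "examine the role of self-efficacy for PA, social support, decisional balance, and collective efficacy as mediators of changes in MVPA".

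Section 6.a, Primary Outcomes (Aim 1 & Aim 2b), plans two things. First, arm averages are compared at each time-point and "ANOVA tests will be performed to evaluate for significant differences between groups". Second, a mixed-effects regression is fitted with measurement occasions nested within women: "Random coefficient modeling will be conducted using random effects variables at level 2 (subject level) that will be both fixed" (nativity, occupation, education, baseline age and so on) and "time varying (perceptions over time, behavior over time, income"). The Secondary Outcomes (Aim 2a) paragraph applies the same mixed model to fitness, BMI and body fat.

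On income, section 6.a, Demographic Variables, states: "Demographic data (collected at baseline only) will be used to describe the study participants". Family income is in that list.

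**The concern.** Aim 1 asks what the programme does to MVPA by whatever route. A covariate measured after randomisation that the programme itself changes absorbs part of that effect. The arm coefficient then describes only what is left once the covariate is held fixed. If the covariate and MVPA also share an unmeasured cause, holding the covariate fixed adds a further bias of its own.

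If the Aim 1 conclusion were drawn from this regression, a programme that works by changing how women perceive barriers, support and opportunities could look weak or ineffective. Because the model is reused, the fitness and body-composition results and the 40-week maintenance results would carry the same problem.

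**Working it through.** **1. Are the covariates measured after randomisation?** Yes, in part. Measurement and Evaluation schedules data at baseline, 16 and 40 weeks, and the table in section 6.d lists the mediator questionnaires three times. Two of the three values of a time-varying perception score therefore follow randomisation.

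**2. Are they on the path from intervention to MVPA?** For perceptions, the protocol's own text points that way:
- The intervention description (D.2.4.2) says that the sessions address perceived barriers and benefits, self-efficacy and social support.
- The environmental-change section has the four intervention centres build a setting that promotes activity.
- The 10-item perceptions scale, meant to "assess environmental supports and capture participants' sense of community opportunities for PA", stands under the heading Mediator Variables.

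Behaviour is not defined in the covariate list.

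**3. Is mediator adjustment planned elsewhere?** Yes. The Mediation Analyses paragraph (Aim 2c) regresses outcome change on arm plus change in the mediator. That is a direct-effect model. Putting the same kind of variable into the Aim 1 model makes its arm coefficient a direct effect too.

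**4. Income.** It is listed as time varying, but section 6.d schedules demographics once. No time-varying income variable can be built from the planned data. This needs no assumption.

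**5. The plan's own sample-size figure.** Inputs from Power and Sample Size: effect 0.50 SD, ICC 0.01, power 0.80, 83 per site, 76% retention, 108 recruited per site; 8 sites. Alpha is not stated. For a cluster-randomised comparison, use a non-central F with 1 and 8 - 2 = 6 df and

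lambda = J d² / (4 [rho + (1 - rho)/n]).

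With J = 8, n = 83, d = 0.50: lambda = 8 × 0.25 / (4 × 0.02193) = 22.80. Power is 0.801 at two-sided alpha 0.01 and 0.976 at 0.05. The smallest n that reaches 0.80 is 83 at alpha 0.01 and 30 at alpha 0.05. So 0.01 reproduces the stated 83, and both levels are shown below.

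**6. Illustration of the size.** Retained per centre: 108 × 0.76 = 82.08, taken as 82, so the bracket is 0.01 + 0.99/82 = 0.02207. The mediated share is an assumption; residual variance and ICC are held unchanged.

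| Share mediated | Coefficient (SD) | lambda | Power, alpha 0.05 | Power, alpha 0.01 |
|---|---|---|---|---|
| 0% | 0.50 | 22.65 | 0.975 | 0.80 |
| 30% | 0.50 × 0.70 = 0.35 | 11.10 | 0.79 | 0.45 |
| 60% | 0.50 × 0.40 = 0.20 | 3.62 | 0.36 | 0.13 |

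**7. Does the shrinkage appear in a model of this type?** A random-intercept model was simulated with 8 sites of 83 women, three occasions, a built-in total effect of 0.50 and 30 replicates per setting. The arm-by-post coefficient averaged:

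| Share mediated | Without the time-varying mediator | With it |
|---|---|---|
| 0% | 0.49 | 0.49 |
| 25% | 0.49 | 0.37 |
| 50% | 0.49 | 0.24 |
| 75% | 0.51 | 0.12 |

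In a single-time regression, an unmeasured cause acting in the same direction on mediator and MVPA (loading 0.3 to 0.5) lowered the adjusted coefficient further: to 0.45-0.37 with nothing mediated, and to 0.20-0.12 with half mediated.

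**The case against.** The strongest reply is that the protocol never calls this regression the primary model. The same paragraph first plans an ANOVA of arm averages at each time-point, which has no post-baseline covariates. This stands. A reader might infer that the trial's primary result is bound to be biased. The documents do not support that, because an unaffected comparison is also planned and nothing ranks the two. What remains is that the regression is the only analysis specified that uses the repeated measures jointly, and that if it and the ANOVA disagree, the protocol does not say which one answers Aim 1.

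The text is also loose. The covariates are given partly as examples, the displayed equation is for a binomial outcome and shows no arm or arm-by-time term, and perceptions are not tied to a named scale. The environmental-supports scale is under Mediator Variables but is not one of the four mediators named in Aim 2c, and that heading also covers depression, stress and diet. So the link to the causal path rests on the session content as well as on the heading. It is strong for perceptions and open for behaviour. A reader might infer that behaviour means physical activity, so that the model would condition on its own outcome. Diet is an equally possible reading, and the document settles neither.

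Finally, a covariate that predicts MVPA would reduce residual variance, so the power losses above are probably overstated. The direction is likely rather than certain: a suppressing mediator, or confounding of opposite sign, could reverse it.

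**Conclusion.** The point holds for the mixed-effects regression. As written, its arm effect would not be the total effect that Aim 1 asks for, and would most likely lie too close to zero. The same applies to Aims 2a and 2b wherever that model is used. Listing income as time varying contradicts the data-collection plan outright.

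The size of the bias cannot be derived from the documents. The fall to 0.35-0.20 SD, with the matching power figures, is an illustration. It rests on an assumed 30-60% mediated share, on an assumed alpha (0.05, or the 0.01 that reproduces 83 per site) and on unchanged residual variance. It should not be read as a finding that the trial is underpowered.

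**What to change.** Delete "time varying (perceptions over time, behavior over time, income") from the models for Aims 1, 2a and 2b. Use baseline covariates only: age, education, nativity, occupation and baseline income.

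Handle baseline MVPA in one of two ways, not both, since using it as response and covariate together would count it twice:
- keep it as a response occasion and read the effect from the arm-by-time terms; or
- adjust for it as a covariate, with only the 16- and 40-week values as responses.

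Name the chosen model as the Aim 1 test and state the role of the ANOVA beside it. Keep post-baseline perceptions and behaviour for the Aim 2c mediation models.

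The cost is a few sentences of analysis text, to be settled before analysis. Data collection, recruitment and sample size are unaffected.

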Mediation Analyses (Aim 2c). As outlined by MacKinnon^{103, 104}, mediation will be assessed by conducting two regression models. The first model will regress change in the hypothesized mediator (e.g., social support, self-efficacy) on intervention group (intervention vs. control) (α coefficient path). The second model will regress change in the outcome variable (e.g., MVPA) on intervention group and change in the hypothesized mediator (β coefficient path). To assess the magnitude of the effect for each potential mediator, the Sobel-Goodman test will be conducted using *sgmediation* in STATA 11 SE¹⁰⁵. This method provides direct and indirect effect estimates, proportion of effect explained by mediator, and significance testing.

Attrition Analyses. We will compare all baseline demographic, cognitive, and behavioral variables of participants lost to follow-up with baseline data of the cohort, to determine possible selective or differential (by treatment condition) attrition. For instance, analyses will be conducted to determine if participants with greater weight or lower PA disproportionately drop out of the study. Selective attrition (i.e., do dropouts differ from the cohort as a whole?) will be considered a threat to external validity or generalization. Presence of differential attrition (i.e., difference in dropouts between treatment conditions) will be considered a threat to internal validity. To the extent that some subjects are lost to follow-up, analysis for the primary and secondary hypotheses will be carried out under the intent-to-treat principle.

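### The one between-arm test named for MVPA is a time-point ANOVA without baseline adjustment, and the regression beside it is shown as a binomial equation with no stated arm contrast

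*Protocol*

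**What the plan says.** All of this stands in the protocol, item 6.a, Quantitative Data Analysis Plan, under Primary Outcomes (Aim 1 & Aim 2b), unless another heading is given.

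- **Outcome.** Both MVPA measures are in minutes: "MVPA outcomes will be self-reported behavior of a typical week measured with the CHAMPS instrument (minutes/week MVPA) and objective measurement from the accelerometer (minutes/day MVPA").
- **Between-arm test.** The arms are compared on visit averages, and "ANOVA tests will be performed to evaluate for significant differences between groups".
- **Change from baseline.** "Assessment will be made to determine direction- e.g. increases or decreases- of change between baseline and post-intervention, and baseline and 6-month follow-up". No between-arm test of that change is named for Aim 1.
- **Regression.** The text then says "we will use a regression that is both multilevel and temporal in nature", and that "time-points of measurement are nested within subjects in a random intercept model". The covariates listed for it are personal characteristics (such as nativity, schooling and age at entry) and time-varying ones (perceptions, behaviour, income).
- **Equation.** The only formula is introduced by "Below we represent the equation for a binomial outcome model". It sets the log of the mean equal to two generic covariate terms. Its levels are repeated MVPA measures and the individual.

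Secondary Outcomes (Aim 2a) carries the same approach over to fitness, BMI and body fat.

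**The concern.** Three things are fixed badly.

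1. The named test ignores each woman's own baseline, although baseline MVPA is measured before randomisation of the CRCs in cohort 1 and at entry in every cohort, and is likely to predict later MVPA.
2. The regression that could use baseline is illustrated by an equation for the wrong kind of outcome. A log-mean coefficient is a ratio of means or proportions. The Power and Sample Size section is built on a standardised difference in means (0.50).
3. The two analyses stand side by side with no statement of which one answers Aim 1. They can give different estimates and different p-values, so the primary result could be chosen after the data are seen.

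In addition, the model's stated levels stop at the subject, while the sample size allows for correlation within CRCs, the randomised unit.

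**Working it through.** **Step 1. The plan's own figure.** Inputs from Power and Sample Size: power 0.80, effect 0.50, ICC .01, 83 per site; 8 CRCs. The significance level is not stated. For a two-arm cluster-randomised F-test:

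λ = J·d² / {4·(ρ + (1−ρ)/n)}, with 1 and J−2 = 6 degrees of freedom.

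At n = 83: λ = 8 × 0.25 / {4 × (0.01 + 0.99/83)} = 2 / 0.0877 = 22.8. Power is 0.80 at two-sided alpha 0.01, so 83 is reproduced at that level. At two-sided 0.05, 30 per site would suffice. With 76% retention, 108 × 0.76 = 82.1 women per CRC. The formula contains no baseline covariate, so the trial is sized for an unadjusted comparison.

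**Step 2. Chance baseline difference between arms.** In SD units, with m women per CRC and 4 CRCs per arm:

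SD = √{2·DE / (4m)}, DE = 1 + (m−1)·ρ.

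| m | DE | SD of difference | P(absolute difference > 0.1) |
|---|---|---|---|
| 82 | 1.81 | √(3.62/328) = 0.105 | 0.34 |
| 108 | 2.07 | √(4.14/432) = 0.098 | 0.31 |

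**Step 3. What reaches week 16.** Only about r times a baseline difference carries over, where r is the baseline-to-follow-up correlation. The protocol gives no r. I assume 0.5, with a range of 0.3 to 0.7, at both participant and CRC level. For a 0.1 SD difference:

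| r | Shift = r × 0.1 | Share of 0.50 | Variance removed = r² | SE after adjustment = 0.105·√(1−r²) |
|---|---|---|---|---|
| 0.3 | 0.03 | 6% | 9% | 0.100 |
| 0.5 | 0.05 | 10% | 25% | 0.091 |
| 0.7 | 0.07 | 14% | 49% | 0.075 |

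**Step 4. Power with baseline adjustment.** With variance multiplied by (1−r²) in the Step 1 formula, n = 83 and two-sided alpha 0.01, power goes from 0.80 to 0.84, 0.91 and 0.98 for r = 0.3, 0.5 and 0.7. The number needed per site falls to 70, 52 and 30. The change does not raise the sample size.

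**Step 5. Does the choice of contrast matter?** This was checked in 30 simulated datasets of 400 women without clustering, with true effect 0.50, within-person correlation 0.5, and a baseline imbalance of 0.20 SD built in as a lasting shift. The follow-up difference alone averaged 0.70. A random-intercept model with an arm-by-time term averaged 0.49. The same model with only an arm main effect averaged 0.55, because that coefficient pools all three visits, baseline included. The lasting shift is harsher than the chance imbalance of Step 3, so these figures show only that the contrasts differ, not the expected size of the problem.

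**The case against.** The strongest reply is that the paragraph already commits to a longitudinal random-intercept model with repeated MVPA as its response. A reader might infer from the ANOVA sentence that baseline MVPA never enters the effect estimate. The text does not support that: baseline is one of the three measurements in the regression. Nor does the schematic equation show that random effects are absent, since the preceding sentences specify a random intercept. Its covariate terms are generic, so arm and arm-by-time are unnamed rather than excluded, and a separate analysis plan may supply them.

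A reader might also infer that minutes of MVPA will be analysed as binomial. The text does not say so. The Stata command is to depend on the structure of the outcome, and transformations of continuous measures are foreseen. The equation is a mismatched illustration.

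The ANOVA is not the only place where arm meets MVPA: Mediation Analyses (Aim 2c) regresses change in MVPA on arm. That serves mediation, not Aim 1.

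Two further readings go too far. Attrition Analyses will "determine if participants with greater weight or lower PA disproportionately drop out of the study", which is a check and not a prediction. That section also promises intent-to-treat, and the plan does not say how the ANOVA treats missing visits, so a completers-only analysis is an inference. GEE is one listed command, not the chosen estimator. And a 0.1 SD imbalance is not a 20% distortion of 0.50. At r = 0.5 that takes a 0.2 SD imbalance, with a probability of about 6% (about 0.2% at r = 0.3, 17% at r = 0.7).

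What stands after this: the equation is wrong for the outcome, the named test is unadjusted, no baseline-adjusted or arm-by-time contrast is named, and neither analysis is designated primary. The first two are statements in this document, not details deferred to another.

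**Conclusion.** The point holds and should be corrected. As written, Aim 1 has an unadjusted time-point ANOVA and a loosely specified regression with a binomial illustration, and no rule for which one counts.

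The size is moderate. The chance baseline difference has an SD of about 0.10 SD. A 0.1 SD difference (31–34% chance) would shift the unadjusted week-16 comparison by 0.05 SD (0.03–0.07), which is 10% (6–14%) of the planned effect. This rests on the plan's ICC of .01 and on an assumed r of 0.3 to 0.7. Under randomisation such imbalance is already part of the sampling error of the unadjusted estimate, so the cost is precision and not bias. No stated sample-size figure depends on it. The larger practical gain is that one analysis, with one named contrast, would answer the primary aim.

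**What to change.** Replace the binomial equation, and the ANOVA as inferential analysis, with one linear mixed model for MVPA minutes (transformed if the distribution requires it), fitted by restricted maximum likelihood:

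- **Responses:** MVPA at weeks 16 and 40.
- **Fixed effects:** arm, time, arm-by-time, cohort, and baseline MVPA as covariate.
- **Random effects:** participant and CRC intercepts.
- **Primary estimate:** the baseline-adjusted arm difference at week 16. The week-40 difference from the same model serves Aim 2b.

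Baseline as covariate is preferable to constraining baseline means to be equal. Under Randomization, each CRC keeps its arm for all three cohorts, so the women of cohorts 2 and 3 (2 × 288 = 576 of 864) enter after their centre's allocation is known.

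Use the same form, with the matching baseline value, for fitness, BMI and body fat. Keep visit means by arm as description only.

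The cost is a change of wording. All data are already to be collected, and the sample size need not rise.
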